### 5.2. General Consideration

The primary analysis of the prognostic value of the MAFA ratio for predicting full aneurysm occlusion 12 months after flow diverter placement will be performed including all subjects who underwent treatment. Baseline patient characteristics and follow-up results will be summarized descriptively using frequencies and percentages or summary statistics like means and medians (including confidence intervals and interquartile ranges). Multiple imputation methods will be used to correct for missing data (Rubin, 1987). All statistical analysis will be performed using R statistical software ([www.r-project.org](http://www.r-project.org))

### 5.3. Subject disposition

Subject disposition, including the total number of subjects evaluated will be presented. In addition, a listing will be provided with the reasons for why the subject was not evaluated.

### 5.4. Primary objective

#### Objective

To assess the prognostic value of the MAFA ratio for predicting full aneurysm occlusion 12 months after flow diverter placement.

#### Endpoint

Philips IGT Systems  Status: Approved	Post-Market Clinical Study Plan  CARO A multicenter observational cohort study	XCY610-130253 2018 Apr 06 Revision: 2.0 Page 17 of 23
--	---	--

The primary endpoint is the prognostic value (i.e. c-statistic including confidence intervals) of the MAFA ratio with respect to full aneurysm occlusion (i.e. Raymond-Roy Occlusion Classification I (Roy *et al.*, 1997) on standard-of-care head imaging) 12 months after flow diverter placement.

#### Experimental design

We will use logistic regression analysis to evaluate the univariate predictive association between the index test (i.e. the MAFA ratio) and complete aneurysm occlusion (i.e. complete occlusion yes/no) at 12 months (Moons *et al.*, 2012). All subjects with complete follow-up will be included in this analysis.

#### Presentation format

The primary endpoint will be presented using an ROC curve including the c-statistic and confidence intervals.

### 5.5. Secondary objectives

#### 5.5.1. Secondary objective: Predictive value at 6 months follow-up

##### Objective

To assess the prognostic value of the MAFA ratio for predicting full aneurysm occlusion 6 months after flow diverter placement.

##### Endpoint

The secondary endpoint is the prognostic value (i.e. c-statistic including confidence intervals) of the MAFA ratio with respect to full aneurysm occlusion (i.e. Raymond-Roy Occlusion Classification I (Roy *et al.*, 1997) on standard-of-care head imaging) 6 months after flow diverter placement.

#### Experimental design

We will use logistic regression analysis to evaluate the univariate predictive association between the index test (i.e. the MAFA ratio) and complete aneurysm occlusion on standard-of-care head imaging at 6 months (Moons *et al.*, 2012). All subjects with complete follow-up will be included in this analysis.

#### Presentation format

This secondary endpoint will be presented using a ROC curves including the c-statistic and confidence intervals.

#### 5.5.2. Secondary objective: Optimal MAFA ratio threshold

##### Objective

To determine optimal MAFA ratio threshold.

##### Endpoint

The endpoint for this secondary analysis is the optimal threshold to make treatment decisions.

#### Experimental design

To determine the optimal threshold for the MAFA ratio, ROC analysis will be performed. The optimal threshold for clinical decision making will be determined using net-benefit analysis (Mallett *et al.*, 2012). Net benefit incorporates estimates of prevalence and misclassification costs, and it is clinically interpretable since it reflects changes in correct and incorrect diagnoses when a new diagnostic test is introduced.

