#### Presentation format

This secondary analysis will be presented within (the legend of) the various ROC curves composed for the primary and secondary objectives.

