##### Experimental design

To explore which clinical variables have (independent) added value for predicting full aneurysm occlusion 6 and 12 months after flow diverter placement we use multivariate logistic regression methods. Candidate predictors (e.g., aneurysm location, size, medication) will be selected based on literature and expert opinion. Then, variable selection (i.e. backward selection using Akaike Information Criteria) will be used to determine the final set of predictors. Finally, internal validation and shrinkage of the model (i.e. using bootstrap methods) will be performed to correct for optimism. Information gained from this exploratory analysis can be used as valuable input for a future clinical prediction model for aneurysm occlusion.

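### Section 5.5.2 plans no interval and no internal validation for the optimal MAFA threshold, a named secondary endpoint, and leaves open the choices that decide how imprecise it is

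*Combined protocol and SAP*

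**What the plan says.** The optimal MAFA threshold is listed among the secondary objectives (Section 3.2) and the secondary endpoints (Summary). Section 5.5.2 defines it by its use: "The endpoint for this secondary analysis is the optimal threshold to make treatment decisions". The method is ROC analysis followed by net benefit: "The optimal threshold for clinical decision making will be determined using net-benefit analysis". The plan adds: "Net benefit incorporates estimates of prevalence and misclassification costs". It gives no value for the costs and no source for the prevalence. On reporting it says: "This secondary analysis will be presented within (the legend of) the various ROC curves composed for the primary and secondary objectives".

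Other analyses in Section 5 are treated differently:

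- Section 5.4 (12 months): "We will use logistic regression analysis to evaluate the univariate predictive association between the index test" and occlusion. For the result: "The primary endpoint will be presented using an ROC curve including the c-statistic and confidence intervals".
- Section 5.5.1 (6 months): "This secondary endpoint will be presented using a ROC curves including the c-statistic and confidence intervals".
- Section 5.6.2 (exploratory multivariable model): "internal validation and shrinkage of the model (i.e. using bootstrap methods) will be performed to correct for optimism".

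Section 4.1 mentions cross-validation as one advantage of using several centers, but nothing in Section 5 carries it out. Section 4.4 expects the study data to help refine MAFA thresholds, and gives each target aneurysm its own sub-form.

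**The concern.** A cut-point chosen from data is an estimate and needs a measure of precision like any other. Here the smaller outcome group is about 20 aneurysms. Followed as written, the report would give one number in a figure legend, and a reader could not tell whether a quite different cut would have fitted almost as well. The intervals in Sections 5.4 and 5.5.1 belong to the c-statistic and say nothing about the location of the cut.

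The second risk is optimism. If the cut is the one that performs best in these subjects, sensitivity, specificity or net benefit at that cut in the same subjects tends to be too favourable. The plan recognises this problem for its exploratory model but not for this secondary endpoint.

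**Working it through.** **Inputs from Section 5.1.** AUC 0.70; ratio of non-occluded to occluded 0.25; one-sided alpha 0.05 (upper percentile); power 0.90; 100 evaluable subjects.

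**The plan's own figure.** A = 0.5244 × 1.414 = 0.7415, so A² = 0.550. V = 0.0099 × exp(-0.275) × [(5 × 0.550 + 8) + (0.550 + 8)/0.25] = 0.338. Then n_D = [1.645 × √(0.0792 × 5) + 1.2816 × √0.338]² / 0.20² = 79.2. This rounds to 80 occluded, plus 20 non-occluded, total 100. The stated figure is reproduced.

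**Assumptions not in the documents.** The marker is equal-variance binormal, oriented so that higher means more likely occluded. Zero is the non-occluded mean and the unit is one within-group SD. The separation is d = 0.5244 × √2 = 0.742. Occlusion is the positive class and each subject has one aneurysm. The threshold probability p is illustrative only (0.7, 0.8, 0.9).

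**Net benefit.** NB = sens × π - w × (1 - spec) × (1 - π), with w = p/(1 - p). The true best cut is d/2 + ln[w(1 - π)/π]/d. With π = 0.80:

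- p = 0.8: w = 4, ln(4 × 0.25) = 0, cut 0.37.
- p = 0.9: w = 9, ln(2.25)/0.742 = 1.09, cut 1.46.
- p = 0.7: w = 2.33, ln(0.583)/0.742 = -0.73, cut -0.36.

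**Simulated 95% range of the cut at p = 0.8.** n = 100, with the number non-occluded varying binomially (95% range 12 to 28).

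| How the cut is found | Prevalence from sample | Prevalence entered as 0.80 |
|---|---|---|
| Maximise sample net benefit | -0.9 to 1.4 SD | -0.6 to 1.2 SD |
| Logistic model at p | -0.6 to 1.2 SD | 0.1 to 0.6 SD |

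**What these ranges mean.** Real sensitivity is Φ(0.742 - cut) and specificity is Φ(cut). At -0.6 they are 0.91 and 0.27; at 1.2 they are 0.32 and 0.88. Across the narrow range they run from 0.74 and 0.54 (cut 0.1) to 0.56 and 0.73 (cut 0.6).

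**Other threshold probabilities.** The narrow cell is special to p = 0.8, which equals the assumed prevalence. With prevalence entered as 0.80, the logistic range is -1.6 to 0.0 at 0.7 and 0.8 to 3.9 at 0.9. Empirical maximisation with the split held at 80/20 gives -1.5 to 0.5 at 0.7 and 0.3 to 2.6 at 0.9.

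**Optimism at p = 0.8 (varying split, sample prevalence).**

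- Empirical: mean net benefit 0.32 apparent, 0.20 real; specificity 0.69 against 0.60; apparent exceeds real in 85% of datasets.
- Logistic: 0.25 against 0.21; specificity 0.63 against 0.62; apparent exceeds real in 57%.

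The size of a net-benefit gap depends on the positive class. With an 80/20 split, empirical maximisation gives 0.31 against 0.21 with occlusion positive, and 0.077 against 0.053 with non-occlusion positive. The second pair times w = 4 returns the first.

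**Does a bootstrap repair it?** 1,000 datasets × 300 patient resamples, varying split, sample prevalence:

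- Percentile-interval coverage at 0.7 / 0.8 / 0.9: logistic 97 / 95 / 95%; empirical 95 / 94 / 78%.
- Net benefit at 0.8, apparent / corrected / real: logistic 0.245 / 0.208 / 0.214; empirical 0.319 / 0.238 / 0.201. The empirical correction removes (0.319 - 0.238)/(0.319 - 0.201) = 0.081/0.118, about two-thirds of the optimism.

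**The case against.** The best counter-argument is that the imprecision is not inherent. The plan already has a univariable logistic model, and net benefit may use an outside estimate of prevalence. At threshold probability 0.8 with prevalence entered as 0.80, the cut is then fairly tight and optimism is negligible. This stands: a reader might infer that the cut must be imprecise however it is found, and the documents do not support that. They name no route, cost weight or prevalence source, and one admissible combination is well behaved. What remains is that the other three combinations at 0.8 are wide, as are both routes at 0.7 and 0.9, and an unreported interval hides which case applies.

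A reader might also infer that the published accuracy will be inflated. The documents do not support that either. They promise no sensitivity, specificity or net benefit at the cut, and the optimism is substantial mainly under empirical maximisation, which they do not specify.

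Nor are the positive class and the time point really missing. Section 5.1 treats occlusion as the condition of interest, Section 5.4 codes the outcome as complete occlusion yes or no, and placing the threshold in the various ROC legends points to both 12 and 6 months.

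Finally, no hypothesis test rests on the threshold, Sections 4.2 and 4.4 say the study neither affects decisions nor recommends management, and an interval could be added later from collected data. This limits the weight of the point. It does not answer it, because the cost weight and the prevalence source lose their value if chosen after the results are seen.

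**Conclusion.** The point holds in a limited form. A named secondary endpoint, defined by its use in treatment decisions, has neither an interval nor internal validation, while the c-statistics have the one and an exploratory model has the other. At threshold probability 0.8 the 95% range of the cut runs from about half an SD wide (0.1 to 0.6) to more than two SD (-0.9 to 1.4), depending on choices the plan leaves open. Optimism is conditional: about 0.12 in net benefit under empirical maximisation (0.32 - 0.20, occlusion positive), smaller under the logistic route, and relevant only where accuracy at the cut is reported or read off the curve.

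These sizes rest on the binormal marker, AUC 0.70, 80% occlusion and the illustrative threshold probabilities. The primary c-statistic needs no cut and is unaffected, as is the sample size. This is a cheap improvement, not a flaw in the main result.

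**What to change.** In Section 5.5.2:

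1. State how the cut is found, preferably from the logistic model of Section 5.4. Fix the threshold probability (or a short range, with its source) and the prevalence source before database lock. No value is proposed here.
2. Extend the bootstrap of Section 5.6.2 to the whole threshold-selection step. Resample patients, since one patient may contribute several aneurysms. The effect is likely small: with an assumed 20% of patients having two aneurysms and a correlation of 0.5, coverage was 94% resampling patients and 93% resampling aneurysms.
3. Report a bootstrap interval for the threshold, and optimism-corrected sensitivity, specificity and net benefit wherever these are given.
4. Reconcile the multiple imputation of Section 5.2 with the restriction to completed follow-up in Sections 5.4 and 5.5.1. If imputation applies to this analysis, say how it is combined with the bootstrap, for example by imputing within each bootstrap sample.

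The cost is SAP wording and modest programming, with no extra data. Reported accuracy will look less favourable. Under empirical maximisation the correction is only partial, and interval coverage falls to about 80% at a threshold probability as extreme as 0.9. With the split held at 80/20, the bootstrap over-corrects the logistic route (net benefit 0.232 to 0.192, against a real 0.229).

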#### Presentation format

This secondary analysis will be presented within (the legend of) the various ROC curves composed for the primary and secondary objectives.

#### 5.5.3. Secondary objective: Adverse events

##### Objective

To register (serious) adverse events (i.e. re-operations, ruptures and deaths).

##### Endpoint

Philips IGT Systems  Status: Approved	Post-Market Clinical Study Plan  CARO A multicenter observational cohort study	XCY610-130253 2018 Apr 06 Revision: 2.0 Page 18 of 23
--	---	--

The endpoint for this secondary analysis is the (total) number of adverse events.

#### Experimental design

The number of adverse events will be described using frequencies and percentages

#### Presentation format

The (total) number of adverse events will be presented in tabular format.

### 5.6. Exploratory objectives

#### 5.6.1. Exploratory objective: Potential value additional AneurysmFlow parameters

##### Objective

- To evaluate the potential value of additional AneurysmFlow parameters for predicting full aneurysm occlusion 6 and 12 months after flow diverter placement.

##### Endpoint

The endpoint of this exploratory objective is the identification of one or more additional AneurysmFlow parameters for predicting full aneurysm occlusion 6 and 12 months after flow diverter placement.

##### Experimental design

To explore which additional AneurysmFlow parameters (e.g. maximum inflow, number of jets) independently contribute to the prediction of, i.e., are associated with, full aneurysm occlusion 6 and 12 months after flow diverter placement predictor finding methods will be used. These methods will be applied to the raw imaging data, collected during the study.

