In Step 3, after FDS deployment, a second DSA run with contrast agent will be acquired (i.e. injection rate  $\approx$ 1.5 to 2 cc/s) at the optimal C-arm viewing angle determined from the 3D-RA to qualitatively evaluate blood motion in the region of the aneurysm after deployment of the FDS. The C-arm angle and injection rate of this second DSA run (post FDS deployment) must be the same as the first DSA run (pre FDS deployment). The 2 DSA runs and the 3D-RA image volume will automatically be sent to the AneurysmFlow workstation right after they are acquired. If the FDS is ballooned after placement, the physician is asked to repeat Step 3 after ballooning.

In Step 4 a routine VasoCT scan, which is another 3D rotational x-ray C-arm scan, will then be performed with the x-ray C-arm in the neuro-interventional suite to evaluate the 3D apposition of the deployed FDS with respect the vessel wall.

The region of interest around the aneurysm and the corresponding arterial segment from which it has developed will be automatically segmented by the AneurysmFlow software, but manual controls are available in the software if modifications to the anatomical segment of interest are desired by the interventionalist. These modifications can be performed by an appropriately trained study member. The software will then automatically calculate the flow parameters of the aneurysm both before and after FDS deployment, along with the MAFA ratio.

For this study, the operator will have the choice of selecting which target aneurysms are amenable to FDS treatment. Patients that have single or multiple target aneurysms that are suitable for FDS treatment as a first treatment step would be acceptable for this study. Each target aneurysm in the patient will have a separate CRF sub-form to fill out. Additionally, each target aneurysm sub-form can be further divided into several FDS sub-forms to account for multiple flow diverters, if needed. To summarize, if the patient has more than one target aneurysm and/or needs more than one flow diverter per aneurysm, then a sub-form on the CRF will need to be filled out for each aneurysm and for each FDS used.

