##### Presentation format

The identified additional AneurysmFlow parameters for predicting full aneurysm occlusion 6 and 12 months after flow diverter placement will be presented in a tabular form, including the strength of the association.

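### Section 5.6.1 equates independent contribution with association and does not require the MAFA ratio in the model, so a flow parameter that merely duplicates MAFA can be listed as an additional predictor

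*Combined protocol and SAP*

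**What the plan says.** Four pieces of the plan bear on this point.

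- **Section 5.6.1, Experimental design.** The aim is to find which additional AneurysmFlow parameters (maximum inflow and number of jets are the examples) "independently contribute to the prediction of, i.e., are associated with, full aneurysm occlusion" at 6 and 12 months. On method it says only that "predictor finding methods will be used", and then: "These methods will be applied to the raw imaging data, collected during the study".
- **Section 5.6.1, Endpoint and Presentation format.** The endpoint is "the identification of one or more additional AneurysmFlow parameters for predicting full aneurysm occlusion". The identified parameters "will be presented in a tabular form, including the strength of the association". No other statistic is promised.
- **Section 4.4, Index Procedure and Discharge.** "The software will then automatically calculate the flow parameters of the aneurysm both before and after FDS deployment, along with the MAFA ratio". The same section defines a final MAFA ratio, which compares flow before any flow diverter with flow after the last one.
- **Section 5.6.2, for contrast.** The clinical-variable objective is worded in terms of added value ("To explore which clinical variables have (independent) added value for predicting full aneurysm occlusion"). It names multivariate logistic regression, backward AIC selection, bootstrap internal validation and shrinkage.

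The MAFA ratio is not mentioned anywhere in section 5.6.1.

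**The concern.** Independent contribution is conditional: does the parameter still carry information about occlusion once the other predictors are known? Association is marginal. The two agree only when the parameter is unrelated to those other predictors. By joining them with an i.e., the plan lets the weaker property stand for the stronger one, and the promised table fits the weaker one.

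This matters because MAFA is the index test of the primary objective, and the other flow parameters come from the same software and the same runs. Some overlap with MAFA is plausible. A parameter that predicts occlusion only because it tracks MAFA has a real marginal association, so bootstrap correction for optimism would not remove it. An analyst who took the gloss literally and filled in the table as described would comply fully with the plan. The resulting list could not separate a parameter that adds information from one that repeats MAFA.

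**Working it through.** **1. Does any text put MAFA in the model for section 5.6.1?** The objective, endpoint, design and presentation paragraphs of 5.6.1 do not. Section 5.1 mentions 8 candidate predictors, AneurysmFlow among them, for the exploratory multivariate analysis. That description fits 5.6.2, the only section that names such a model. Even there, backward AIC selection is free to drop MAFA. The gap in 5.6.1 is not filled elsewhere.

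**2. Scale, from the plan's own sample size.** Section 5.1 gives kappa = 0.25, AUC 0.70, alpha 0.05 and beta 0.10. With z_alpha read as the upper 5% point (1.645):

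- A = 0.5244 × 1.414 = 0.7415, so A² = 0.550
- V = 0.0099 × exp(−0.275) × [(5 × 0.550 + 8) + (0.550 + 8)/0.25] = 0.338
- n_D = [1.645 × √(0.0792 × 5) + 1.2816 × √0.338]² / 0.20² = 79.23
- Total = 79.23 × 1.25 = 99.03. Rounding up by group gives 80 + 20 = 100, the plan's figure.

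The illustration therefore uses 80 occluded and 20 non-occluded.

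**3. A parameter with nothing to add.** Let X be MAFA, oriented so that higher values go with occlusion (the sign is immaterial). X is normal with variance 1 in each class. The class means differ by d = √2 × 0.5244 = 0.742, which gives AUC 0.70. Let the extra parameter be Z = ρX + √(1 − ρ²) × noise. Given X, Z carries no information about occlusion, and its correlation with X within outcome class is ρ. Its own AUC is Φ(ρd/√2). **ρ is an assumption**, because the documents give no value.

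**4. Listing rates.** 4,000 simulated studies were run per ρ, with likelihood-ratio tests of Z alone and of Z with X in the logistic model. The p<0.05 rule (LR > 3.841) is illustrative, as 5.6.1 states no rule. The AIC rule (LR > 2) is borrowed from 5.6.2.

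| ρ | AUC of Z alone | p<0.05: Z alone | p<0.05: given MAFA | AIC: Z alone | AIC: given MAFA |
|---|---|---|---|---|---|
| 0 | 0.500 | 5.5% | 5.0% | 16% | 16% |
| 0.3 | 0.563 | 15.5% | 5.5% | 33% | 18% |
| 0.5 | 0.603 | 32.8% | 5.7% | 54% | 17% |
| 0.7 | 0.643 | 53.5% | 5.5% | 74% | 17% |
| 0.8 | 0.663 | 65.3% | 5.6% | 83% | 17% |
| 0.9 | 0.682 | 76.5% | 5.3% | 90% | 17% |

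A separate run of the same size gave 33.5, 54.5, 64.7 and 76.1% (Z alone, p<0.05) for ρ = 0.5, 0.7, 0.8 and 0.9. The two runs agree to about one percentage point, in line with a simulation standard error of at most √(0.25/4000) = 0.8 points.

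These are 12-month figures. The plan gives no expected occlusion ratio at 6 months, so the rates do not carry over to that analysis.

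**The case against.** The strongest reply is that the plan does not prescribe an unadjusted screen. A reader might infer from the i.e. that redundant parameters will be listed. The documents do not support that. The method is unnamed, the word *independently* is there, and a multivariable model containing MAFA would comply just as well. An adjusted odds ratio is also a strength of association. This stands: the defect is that the text permits the weaker analysis, not that it mandates it.

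Second, the objective speaks of additional parameters without naming MAFA, and *additional* could simply mean other than MAFA. On that reading a correlated predictor still meets the stated objective and endpoint. The wording allows this, but it leaves *independently* with nothing to do. The plan should say which question it is asking.

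Third, strong correlation with MAFA is not documented. A shared source does not make a count of jets a restatement of a before/after quotient. This also stands. At ρ = 0 there is no problem, and at 0.3 it is modest, which is why the whole range is shown.

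Fourth, a reader might infer that parameters listed here go forward into later use. The remark about input to a future prediction model is in 5.6.2, not 5.6.1, and section 4.4 says the study makes no recommendation on patient management.

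**Conclusion.** The concern holds as a matter of what the plan permits. Section 5.6.1 equates two different properties, names no method and does not require the MAFA ratio in the model. A compliant analysis can therefore present a duplicate of MAFA as an additional predictor.

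Under association-only screening at p<0.05, the chance of listing a parameter with no information beyond MAFA runs from the nominal level (about 6%) at ρ = 0 to about 77% at ρ = 0.9. With MAFA in the model it stays at 5 to 6% throughout. These rates rest on an assumed correlation, normal distributions with MAFA AUC 0.70, the 80:20 split at 12 months, and a selection rule the plan does not state. They show direction and scale and do not forecast the study's result.

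Only an exploratory objective is affected. The change is worth making, but the primary endpoint, the secondary endpoints and the sample size do not depend on it.

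**What to change.** In section 5.6.1:

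- Delete the gloss that equates independent contribution with association.
- Name the method: judge each candidate parameter in a logistic model that always contains the final MAFA ratio as defined in section 4.4, separately at 6 and 12 months.
- Base identification on the contribution given MAFA, by a likelihood-ratio test or change in AIC, and state which.
- In the table, give the MAFA-adjusted odds ratio and the change in c-statistic over MAFA alone, each with a confidence interval. Unadjusted associations can stay as a descriptive column.

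The cost is a wording change and one extra term per model, with no new data. The downside is that fewer parameters will be named. With about 20 non-occluded cases, a parameter that truly adds information will also be harder to detect once MAFA is in the model.

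### Section 5.6.1 selects additional AneurysmFlow parameters and reports their strength from the same data with no planned optimism correction, although section 5.6.2 plans one

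*Combined protocol and SAP*

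**What the plan says.** Section 5.6.1 sets as its endpoint the "identification of one or more additional AneurysmFlow parameters for predicting full aneurysm occlusion 6 and 12 months after flow diverter placement". Its experimental design asks which "additional AneurysmFlow parameters (e.g. maximum inflow, number of jets) independently contribute to the prediction of" full occlusion. The candidates are given by two examples, without a number or a closed list. The method is that "predictor finding methods will be used", and on the data it adds: "These methods will be applied to the raw imaging data, collected during the study". Under its presentation format, the parameters found "will be presented in a tabular form, including the strength of the association".

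Section 5.6.2 deals with clinical variables and the same two occlusion outcomes. It draws its candidates from literature and expert opinion, names "backward selection using Akaike Information Criteria" as the selection rule, and then states that "internal validation and shrinkage of the model (i.e. using bootstrap methods) will be performed to correct for optimism". Its endpoint is the model after shrinkage.

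Section 5.1 plans for 100 evaluable subjects and four occluded aneurysms to each non-occluded one at one year. The limit of 8 candidate predictors given there is for the multivariate analysis. No limit is set for the search in 5.6.1.

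**The concern.** When the same patients are used to pick parameters and to estimate their strength, the picked parameters look stronger on average than they are, because favourable chance variation helped them to be picked. The effect grows with the number of candidates and shrinks with the size of the smaller outcome group, which is small here. The plan recognises the problem in 5.6.2 and provides for it. It does not do so in 5.6.1, where the search is less constrained: candidates are not filtered in advance and no rule for keeping one is given.

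At stake is what a reader takes from the 5.6.1 table. A flow parameter listed as identified, at its apparent strength, may be carried into a later prediction model or software development on evidence weaker than it looks.

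**Working it through.** **1. Size of the smaller outcome group.** Inputs from section 5.1: AUC θ = 0.70, κ = 0.25, type I error 0.05, power 0.90. The plan's formula, with z taken one-sided as the plan defines it:

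- A = 0.5244 × 1.414 = 0.7415, and V(θ) = 0.338.
- n_D = [1.645 × √(0.0792 × 5) + 1.282 × √0.338]² / 0.20² = 79.23.
- Total = 79.23 × 1.25 = 99.03. Rounding up by group gives 80 + 20 = 100.

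The planned 100 therefore reproduces, with 20 non-occluded. If all 120 enrolled were evaluable, the figure would be 24. Both are 12-month planning figures; the plan gives no 6-month occlusion rate.

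**2. Chance of at least one false selection, independent candidates.** Assumed, because the plan does not state them: k = 5, 10 or 20 candidates with no true value, each kept if its p-value is below c. The formula is 1 − (1 − c)^k. Two values of c are shown: 0.05, and 0.157, which is roughly what AIC implies for a single parameter. AIC is the rule of 5.6.2, not of 5.6.1.

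| k | c = 0.05 | c = 0.157 |
|---|---|---|
| 5 | 1 − 0.95^5 = 23% | 1 − 0.843^5 = 57% |
| 10 | 40% | 82% |
| 20 | 64% | 97% |

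With only the two parameters that the plan names as examples, the figures are about 10% and 29%. These are for one time point. Section 5.6.1 covers two, which raises them, but the 6- and 12-month outcomes are correlated, so the increase cannot be computed as if they were independent.

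**3. Correlated candidates.** The parameters come from the same images, so correlation is plausible. Simulation with 80 occluded and 20 non-occluded, for 5 to 20 candidates:

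| Assumed pairwise correlation | p<0.05 | p<0.157 |
|---|---|---|
| 0.5 | 18% to 44% | 49% to 86% |
| 0.8 | 13% to 23% | 36% to 56% |

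Simulation error is one to two percentage points.

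**4. Apparent strength of the best noise parameter.** Same 80:20 simulation, direction of effect left free, true AUC 0.50. The mean best apparent AUC is 0.61, 0.64 and 0.66 for 5, 10 and 20 independent candidates (0.58 for 2). At a correlation of 0.8 it is 0.59 to 0.62. With independent candidates it reaches the planned 0.70 in about 3% to 10% of studies.

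**5. A parameter with some real value.** A true AUC of 0.60, reported only when p<0.05, shows a mean of 0.68; it is selected in 28% of studies.

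**6. What a bootstrap would aim to remove.** One real predictor (AUC 0.70), the remaining candidates noise, backward AIC selection:

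| Candidates in total | Apparent AUC | AUC in new data | Gap |
|---|---|---|---|
| 5 | 0.72 | 0.67 | 0.04 (before rounding) |
| 8 | 0.75 | 0.65 | 0.09 (before rounding) |
| 12 | 0.77 | 0.64 | 0.13 |

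**The case against.** The strongest reply is that 5.6.1 is underspecified rather than wrong. It names no method in detail, so it does not rule out internal validation, and the size of any inflation cannot be derived from it. That stands as to size: every percentage above depends on an assumed number of candidates, selection rule and correlation. It does not remove the point. The design and presentation paragraphs together describe selection followed by a table of strengths from the same data, and the correction that 5.6.2 spells out is absent.

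A second reply is that the outputs differ. Section 5.6.2 produces a model with calibration and discrimination, for which shrinkage is usual, while 5.6.1 produces a list of associations. This partly explains the different treatment, so the contrast is not a contradiction in itself. But reporting a list "including the strength of the association" is still reporting effect sizes after selection, and the bias applies to them.

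A third is that section 4.1 says the multicentre design allows cross-validation of results. That is a general remark; no analysis in section 5 carries it out.

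A reader might also infer that chance findings would look about as good as the AUC of 0.70 for which the study is sized. The documents do not support that. The average best noise AUC stays below 0.70 and only the upper tail reaches it. Section 5.6.1 does not commit to reporting an AUC at all; it is used here as a common scale.

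**Conclusion.** The point holds as a minor one. Followed as written, 5.6.1 reports post-selection strengths with no planned correction, and these are inflated in expectation. The documents do not determine by how much. For 5 to 20 candidates without true value and a 20-case smaller group, the chance of at least one false selection runs from 13% (p<0.05, correlation 0.8, 5 candidates) to 97% (p<0.157, independent, 20 candidates). The mean best apparent AUC runs from 0.59 to 0.66. Fewer candidates would give lower figures.

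The 20 non-occluded cases rest on the 12-month planning ratio and should not be carried over to the 6-month analysis. The objective is labelled exploratory, and the primary c-statistic for the MAFA ratio is not affected.

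**What to change.** In section 5.6.1:

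1. List the candidate AneurysmFlow parameters and state the selection rule before the analysis. This must come first, because a search that is not defined cannot be repeated in a resample.
2. Repeat the whole selection in each bootstrap resample, not only the refitting of the parameters finally chosen.
3. Report optimism-corrected strengths, how often each parameter is selected across resamples, and the number of parameters searched, at each time point.
4. Label the results hypothesis-generating.

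The cost is modest extra analysis work. The approach follows 5.6.2, but the bootstrap planned there is for a backward-AIC logistic model and would have to be adapted to the search in 5.6.1. No further patients or data are needed. The reported associations will be weaker.
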